8.3.5 Pregnancy Test

Pregnancy testing information captured on the CRF will be presented in a listing for the safety population.

8.3.6 Family History

Family history information captured on the CRF will be presented in a listing for the safety population.

8.3.7 Electrocardiogram

ECG data captured on the CRF will be presented in a listing for the safety population.

8.3.8 MMSE & OSU TBI-ID

MMSE and OSU TBI-ID information captured on the CRF will be presented in listing.

8.4 Analysis of Efficacy Parameters

8.4.1 Analysis of Primary Efficacy Variable

8.4.1.1 Quantitative Assessment of Images

The MUBADA SUV_r (as described in section 6.4.1.1) from the available imaging visits will be summarized using descriptive statistics (n, mean, SD, min, max, and median) for the efficacy population by cognitive groups (CI and CN). An analysis of covariance (ANCOVA) model will be used to test significant differences in baseline MUBADA SUV_r between the two cognitive groups adjusted for age. All descriptive statistics, including LSM (+/- SE), LSM differences (95% C.I.), and p-values will be reported in a table.

MUBADA SUV_r will also be presented in a scatter plot by clinical group.

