4.2 Method of Assignment of Subjects to Treatment and Diagnosis Groups

Subjects who qualified for the study received a single IV bolus injection with a target dose of 240 (6.49 mCi) or 370 MBq (10 mCi) of flortaucipir (¹⁸F) injection.

Subjects will be classified into diagnosis groups (Alzheimer’s disease AD [AD], mild cognitive impairment [MCI], control subject [CN], other dementing disorder [ODD], other neurological disorder [OND], psychiatric disorder [PD]) as outlined by pre-specified criteria (see protocol amendment 1, appendix 11.3 for details), however there was no design (adaptive or otherwise) to stratify an equal number of subjects in each diagnosis group. Diagnosis groups will be consolidated in the following way in the result summaries.

Table 2: Consolidation of Diagnosis Groups for Presentation of Results

Diagnosis Group	Presentation Group
AD	Cognitively Impaired (CI)
MCI	
ODD	
OND	
PD	
CN	Cognitively Normal (CN)

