4.4 Determination of Sample Size

No power or sample size calculation was done for this study as there was no hypothesis for testing per study objectives. Approximately 179 subjects including healthy controls and subjects at risk for tau accumulation as defined by the sites' companion protocols were dosed with flortaucipir and underwent a PET scan.

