7.1.3 Type I Error

Unless otherwise specified, hypothesis testing will be two-sided with type I error rate of 0.05.

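### The age-adjusted ANCOVA of CI versus CN uses one residual variance, so its standard errors and confidence interval are wrong if the pooled CI group is more variable

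*SAP*

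**What the plan says.** SAP 8.4.1.1 compares the CI and CN groups on the primary efficacy variable: "An analysis of covariance (ANCOVA) model will be used to test significant differences in baseline MUBADA" SUVr "between the two cognitive groups adjusted for age". The table of results is to contain all descriptive statistics, "including LSM (+/- SE), LSM differences (95% C.I.), and p-values will be reported in a table". The section names no SAS procedure, variance structure, robust standard error or check of assumptions, and nothing elsewhere in the SAP does so.

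SAP 4.2, Table 2, forms CI from AD, MCI, other dementing disorder, other neurological disorder and psychiatric disorder. CN stands alone. On group sizes the same section says: "however there was no design (adaptive or otherwise) to stratify an equal number of subjects in each diagnosis group".

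SAP 4.4 gives the sample as "Approximately 179 subjects including healthy controls and subjects at risk for tau accumulation" and states: "No power or sample size calculation was done for this study as there was no hypothesis for testing per study objectives". SAP 7.1.3 nevertheless sets a general rule that "hypothesis testing will be two-sided with type I error rate of 0.05".

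**The concern.** An ordinary ANCOVA estimates one residual variance and uses it for both groups. That is safe if SUVr varies about equally in CI and CN after age adjustment, and there are reasons to doubt it here.

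- CI mixes five diagnoses. The introductions to both documents describe strong signal in tau-positive tissue and weak or no binding in tau-negative tissue, so CI may combine high-uptake and low-uptake subjects.
- CN is narrowly defined in Protocol Appendix 11.3: MMSE of at least 29, with normal history and psychometric testing.

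If CI is more variable, the pooled variance lies between the two true variances. The CI mean then looks more precise than it is and the CN mean less precise, whatever the split. For the difference, the two errors cancel only when the groups are of similar size. The interval is too narrow if CI is the smaller group and too wide if it is the larger. What is at stake is the accuracy of the reported standard errors, interval and p-value, not the point estimate.

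**Working it through.** **Inputs.** From the SAP: N about 179 (4.4), which is an upper bound for the efficacy population; two-sided 0.05 (7.1.3); covariate age only (8.4.1.1). The documents give no SUVr SDs and no CI/CN counts, so there is no figure of the plan's own to reproduce. Assumed: CN residual SD of 1, CI:CN SD ratio *r* of 1, 1.5, 2 or 3, and CI counts of 45, 60, 90, 119 or 134 out of 179.

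**Formulas**, for groups with similar age distributions, with n₁ for CI and n₂ for CN:

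- Pooled variance: s² = [(n₁ − 1)r² + (n₂ − 1)] / (n₁ + n₂ − 2)
- Model SE ÷ true SE for the CI mean: s/r; for the CN mean: s
- Model SE ÷ true SE for the difference: k = √{ s²(1/n₁ + 1/n₂) / (r²/n₁ + 1/n₂) }
- Coverage of the nominal 95% interval: about 2Φ(1.9735·k) − 1. This gives 95.2% when k = 1, so it reads about 0.2 points high.

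**Worked example, 45/134, r = 2.**

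- s² = (44 × 4 + 133)/177 = 309/177 = 1.746, so s = 1.321
- CI mean: 1.321/2 = 0.66; CN mean: 1.32
- Difference: model variance 1.746 × (1/45 + 1/134) = 0.0518; true variance 4/45 + 1/134 = 0.0964; k = √(0.0518/0.0964) = 0.73
- Coverage: about 85%

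**Worked example, 90/89, r = 2.** s² = (89 × 4 + 88)/177 = 2.508 and s = 1.584. The CI mean ratio is 0.79, the CN mean ratio 1.58, and k = 1.00.

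**All cells.** Each entry gives model SE ÷ true SE for the CI mean / CN mean / difference, then coverage of the interval for the difference.

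| CI/CN | r = 1.5 | r = 2 | r = 3 |
|---|---|---|---|
| 45/134 | 0.76 / 1.14 / 0.82; 89.6% | 0.66 / 1.32 / 0.73; 85.2% | 0.58 / 1.73 / 0.65; 80.3% |
| 60/119 | 0.79 / 1.19 / 0.88; 91.7% | 0.71 / 1.41 / 0.82; 89.3% | 0.64 / 1.91 / 0.76; 86.7% |
| 90/89 | 0.85 / 1.28 / 1.00; 95.2% | 0.79 / 1.58 / 1.00; 95.2% | 0.75 / 2.24 / 1.00; 95.3% |
| 119/60 | 0.90 / 1.35 / 1.14; 97.5% | 0.87 / 1.73 / 1.22; 98.4% | 0.84 / 2.52 / 1.31; 99.0% |
| 134/45 | 0.93 / 1.39 / 1.21; 98.3% | 0.90 / 1.80 / 1.36; 99.3% | 0.88 / 2.65 / 1.53; 99.7% |

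At r = 1 every SE ratio is 1.00.

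**Effect of age imbalance.** If CI is 5 years older on average (age SD 8), the difference ratios move by at most about 0.07. The CN-mean ratio at 90/89 becomes 1.26 to 2.05 instead of 1.28 to 2.24. If the age spread also differs between the groups, the difference ratio near 1:1 runs from 0.96 to 1.05 at r = 2.

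**Simulated coverage for the difference, r = 2** (5,000 trials per cell, 5-year age gap, age SD 8):

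| CI/CN | Ordinary ANCOVA | HC3 | Separate variances |
|---|---|---|---|
| 45/134 | 85.4% | 94.4% | 94.1% |
| 60/119 | 89.4% | 94.9% | 94.7% |
| 90/89 | 94.7% | 94.8% | 94.7% |
| 119/60 | 97.9% | 95.5% | 95.4% |
| 134/45 | 99.1% | 95.5% | 95.3% |

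At r = 1 all three methods gave 94.3% to 95.3%.

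**Skewed CI values.** A second simulation (4,000 trials per cell, age SD 10) also let 30% or 10% of CI subjects be shifted upward to produce the same SD ratios. Bias of the difference was at most 0.012 CN SD. With the 10% shift, the hardest case, coverage over the five splits was 92.7% to 95.4% for HC3 and 92.9% to 95.2% for separate variances. At a stress split of 36/143 the two remedies gave 92% to 95%, against 75% to 88% for ordinary ANCOVA.

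**The case against.** The strongest reply is that the error depends on two quantities the documents do not give. Pooling five diagnoses raises the variance only if their SUVr distributions differ. The companion studies named include aging, depression and traumatic brain injury, so CI might consist mainly of subjects with uptake close to CN. The interval for the difference fails to cover only if CI is both more variable and smaller, and nothing places the trial there. This stands, and it is why the result is conditional.

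The r = 3 column is also demanding. If a fraction p of CI is shifted by d CN SDs, then r² = 1 + p(1 − p)d². With p = 0.10, r = 3 needs d = √(8/0.09) = 9.4; with p = 0.30 it needs √(8/0.21) = 6.2. At r = 1.5 the shifts are 3.7 and 2.4. The r = 3 figures should be read as an outer bound.

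Inflated type I error is not the main harm. It needs equal means despite unequal spread, whereas a high-uptake subset would move the mean as well.

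The SAP states no hypothesis, and the protocol's efficacy analysis (8.2.1) is descriptive. That limits the consequence, but SAP 8.4.1.1 still commits to standard errors, an interval and a p-value, and these should be right. The planned group SDs and scatter plot would reveal unequal spread without correcting the adjusted results.

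Finally, separate variances do not make the mean of a five-diagnosis mixture easier to interpret. That is true, but it is a separate matter.

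**Conclusion.** The point holds as a conditional weakness of the planned model. If residual SUVr spread is larger in CI, the standard error of the CI mean is too small and that of the CN mean too large at every split examined. The interval for the difference is also wrong unless the groups are of similar size. For SD ratios of 1.5 to 3 and N = 179, calculated coverage is about 80% to 90% at 45/134, nominal at 90/89, and about 98% to 99.7% at 134/45. If the SD ratio is 1 there is no error. The estimated difference is essentially unaffected. The change is worth making because it costs almost nothing. Its priority is modest because no decision rule uses the test.

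**What to change.** Add to SAP 8.4.1.1:

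> The age-adjusted model will be fitted with separate residual variances for the CI and CN groups (SAS PROC MIXED, REPEATED / GROUP= cognitive group, Satterthwaite degrees of freedom). LSM standard errors, the 95% confidence interval for the LSM difference and the p-value will be taken from this fit.

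Kenward-Roger degrees of freedom or HC3 standard errors would also serve, but the SAP should name one method in advance.

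The cost is one sentence and one code option, with no extra data or subjects. When variances were in fact equal, the simulated 95% interval was 0 to 0.7% wider with separate variances and 0.8 to 1.0% wider with HC3, and coverage stayed at about 95%. One limit remains: with strongly skewed CI values and a small CI group, coverage can still fall to about 92% to 93%.

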5.2. Selection of Subjects

Subjects should meet inclusion and exclusion criteria for the companion protocol, and in addition:

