7. PROCEDURES AND METHODS

7.1. Assessment Periods (See Section 11.2, Trial Flow Chart)

The study will consist of the following sequence of activities:

7.1.1. Screening:

Screening may take place over several days. All screening assessments will preferably be performed within 30 days prior to the PET imaging session. Some screening assessments may be performed on the imaging day prior to injection with sponsor approval.

Screening assessments will include:

- Informed consent;
- Demographics (age, gender, education, race, ethnicity);
- Medical history, concomitant medications;
- Disease history (date/months since symptom onset, date/months since diagnosis, family history of relevant neurologic disease);
- An ECG will be performed to assess the subject's cardiac status. If an ECG was performed within the last 6 months and is available for review, the ECG does not need to be repeated;
- Cognitive status interview, including MMSE and OSU TBI-ID;
- Where appropriate, informant interview with family member or close friend who is familiar with subject's everyday functioning abilities;
- Urine or serum pregnancy test (women of childbearing potential);
- A physician will see the patient during the screening visit.

Demographic information, cognitive status assessment, MMSE, and OSU TBI-ID collected within the last 60 days as part of a companion protocol or clinic visit need not be repeated.

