8. STATISTICAL ANALYSIS

8.1. General Statistical Considerations

All statistical analyses will be performed using SAS® version 8.2 or higher.

All values will be summarized by diagnostic group: cognitively normal volunteers, patients with AD, patients with MCI and where relevant, other disorders as determined by the companion protocol. Guidelines for diagnostic classification of cognitively normal volunteers, subjects with MCI and subjects with AD can be found in Appendix 11.3.

Frequency distributions including counts and percentages will be included for all categorical outcome variables. All continuous outcome variables will be summarized with statistics including mean, standard deviation, median, minimum and maximum values.

All data from the electronic case report forms (eCRFs) as well as any derived variables will be presented by listings.

Additional details concerning statistical analyses will be included in the Statistical Analysis Plan (SAP) to be completed prior to the end of enrollment into the study.

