6.4 Efficacy Variables

6.4.1 Primary Efficacy Variable

6.4.1.1 Flortaucipir Quantitation

Standard uptake value ratios (SUVr) will be calculated to estimate tau load globally and in individual regions for the flortaucipir images. A target region derived statistically with a Multiblock Barycentric Discriminant Analysis (MUBADA) method will be used for the global measurement.

Voxels of interest determined in the automated anatomical labeling (AAL) atlas masked to exclude white matter and CSF for amygdala, anterior fusiform, posterior fusiform, anterior hippocampus, posterior hippocampus, anterior parahippocampus, posterior parahippocampus, caudate, frontal, parietal, precuneus, temporal, occipital, left frontal, right frontal, left occipital, right occipital, left parietal, right parietal, left putamen, right putamen, left temporal, right temporal will be applied at the individual region level. A selected white matter region derived using a parametric estimated signal reference intensity (PERSI) method will be used as reference region for all SUVr calculations.

MUBADA SUVr will be the variable used in in the primary efficacy analysis.

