8.3 Baseline Subject Data

8.3.1 Demographic and Other Baseline Characteristics

All baseline summaries will be based on the safety population. Age (years), gender, race, ethnicity, education, and MMSE will all be summarized in a table and presented in a listing.

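### The only CI versus CN model for MUBADA SUVr adjusts for age alone; adding sex as a covariate is a cheap safeguard against possible confounding

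*SAP*

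**What the plan says.** SAP 6.4.1.1 states that "MUBADA SUVr will be the variable used in in the primary efficacy analysis". SAP 8.4.1.1 summarises that variable by cognitive group and fits one inferential model, an ANCOVA comparing CI with CN, with the difference tested "between the two cognitive groups adjusted for age". It reports least squares means, their difference with a 95% confidence interval, and p-values. The SAP describes no second model with other covariates, and section 7.6 rules out subgroup analyses.

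Subjects reach the study through the sites' own companion studies. Protocol 5.2 opens its criteria with "Subjects should meet inclusion and exclusion criteria for the companion protocol, and in addition". On allocation to diagnosis groups, SAP 4.2 says "there was no design (adaptive or otherwise) to stratify an equal number of subjects in each diagnosis group", and its Table 2 pools AD, MCI and three other categories into CI.

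Sex is among the planned data. Protocol 7.1.1 lists "Demographics (age, gender, education, race, ethnicity" at screening, and SAP 8.3.1 says "Age (years), gender, race, ethnicity, education, and MMSE will all be summarized in a table and presented in a listing". Protocol 8.1 adds that "All values will be summarized by diagnostic group".

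**The concern.** CI and CN are observed groups, so any characteristic that differs between them and also relates to SUVr can distort the comparison. By adjusting for age, the SAP accepts that baseline demographics may need to be held constant, but it gives no reason for stopping at age. Sex is an obvious second candidate. It precedes diagnosis, so adjusting for it does not remove an effect that runs through disease. It is also already on the collection list and takes one degree of freedom.

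At stake is the reading of the adjusted CI minus CN difference, its interval and its p-value. If both conditions for confounding held, part of a sex difference would be reported as a difference by cognitive status. The baseline table might reveal the imbalance, but no planned model would correct for it.

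**Working it through.** **Inputs from the documents.** About 179 subjects dosed and scanned (SAP 4.4); two-sided 0.05 tests (SAP 7.1.3); age as the only covariate (SAP 8.4.1.1). The plan has no power figure, SD or expected difference to reproduce.

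**Assumptions, because the documents are silent.** The CI:CN split, the sex mix in each group, and the sex effect on SUVr given age and group. Effects are in units of the residual SD of SUVr.

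**1. Bias.** With sex omitted,

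bias = (sex effect on SUVr given age and group) × (difference in proportion male between CI and CN, given age).

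It is a product, so it vanishes if either factor is zero.

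**2. Effect on the 95% interval.** Take a 120:59 split. SE = √(1/120 + 1/59) = 0.159 SD. Coverage = Φ(1.96 − bias/SE) − Φ(−1.96 − bias/SE).

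| Sex effect (SD) | Imbalance (points) | Bias (SD) | Coverage |
|---|---|---|---|
| 0 | any | 0 | 95% |
| any | 0 | 0 | 95% |
| 0.1 | 20 | 0.1 × 0.20 = 0.02 | 94.8% |
| 0.25 | 40 | 0.25 × 0.40 = 0.10 | 90.4% |
| 0.4 | 40 | 0.4 × 0.40 = 0.16 | 82.8% |

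**3. A different split and smaller imbalances.** With an even split, SE = √(2/89.5) = 0.149 SD. Actual type I error = Φ(−1.96 + bias/SE) + Φ(−1.96 − bias/SE). Sex effects of 0.1 to 0.5 SD give:

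- 10 points: bias 0.01 to 0.05 SD, error 0.051 to 0.063
- 20 points: bias 0.02 to 0.10 SD, error 0.052 to 0.103
- 30 points: bias 0.03 to 0.15 SD, error 0.055 to 0.171

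With a 30:70 split, the worst of these (30 points, 0.5 SD) falls to 0.151.

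**4. Check by simulation.** 4,000 runs per case, groups of 90 and 89, no true group difference, residual SD 1, an age slope of 0.3, and CI older by 0.3 SD of age.

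| Imbalance, sex effect | Age only: bias, error | Age and sex: bias, error |
|---|---|---|
| 20 points, 0 | −0.001, 0.047 | −0.001, 0.046 |
| 0 points, 0.5 SD | −0.002, 0.052 | −0.002, 0.052 |
| 20 points, 0.2 SD | 0.040, 0.064 | 0.000, 0.053 |
| 20 points, 0.5 SD | 0.102, 0.101 | 0.001, 0.054 |
| 30 points, 0.5 SD | 0.154, 0.164 | 0.005, 0.047 |

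The Monte Carlo error on a rate near 0.05 is √(0.05 × 0.95/4000) = 0.003. The simulation agrees with the formula, and adding sex removes the bias.

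**5. Cost in precision if sex is unrelated to SUVr.** SE inflation = 1/√(1 − r²), where r is the correlation between group and sex. At 120:59 and 50% male overall, r = imbalance × √(0.670 × 0.330)/0.5 = 0.94 × imbalance. A 20-point imbalance gives r = 0.188 and inflation 1.018. A 40-point imbalance gives r = 0.376 and inflation 1.079. In the simulation at 20 points with no sex effect, the SE rose from 0.1515 to 0.1551. Where sex does matter the SE can fall: at 0 points and 0.5 SD it went from 0.1559 to 0.1516.

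**The case against.** The strongest reply is that an age-only model is a legitimate pre-specified choice and that the documents contain nothing to single out sex. They report no sex effect on SUVr and no sex distribution by group. Education, race and ethnicity sit in the same list and could be argued for in the same abstract way. Little depends on the p-value either: SAP 4.4 says the objectives carry no hypothesis to test, there is no power calculation, and protocol 8.2.1 plans only descriptive statistics for tau. An imbalance would also be visible, since gender is tabulated and protocol 8.1 asks for summaries by diagnostic group.

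Most of this stands. The comparison is exploratory, age-only adjustment is defensible, and the case for sex rests on low cost rather than on evidence in the documents. What remains is that the difference, interval and p-value will still be reported, and that seeing an imbalance does not correct for it.

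A reader might also infer more than the documents support:

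- *Any sex imbalance passes directly into the SUVr difference.* It does not. Without a sex effect given age and group, even a large imbalance gives no bias.
- *The groups are unmatched, or come from different companion protocols.* The SAP 4.2 sentence concerns the number in each diagnosis group, not matching on sex. The companion protocols are not supplied, and one cohort could provide both groups. The supportable statement is that no balancing on sex is described.
- *Sex is complete for every subject.* Protocol 7.1.1 is a collection plan and does not report completeness.

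**Conclusion.** The point holds as a modest improvement. The single between-group model adjusts for age only, the groups are not randomised, no balancing on sex is described, and the variable needed is already planned for collection. Under assumed sex effects of 0.1 to 0.4 SD and assumed imbalances of 20 to 40 points, the bias is 0.02 to 0.16 SD. At an assumed 120:59 split, coverage of the nominal 95% interval is then between 94.8% and about 83%. The lower figure needs the most extreme pairing, such as 70% against 30% male with a 0.4 SD sex effect. At a 10-point imbalance the bias is at most 0.05 SD even with a 0.5 SD sex effect.

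The documents do not support calling the age-only model an error, or saying that the reported difference will be biased. They support saying that it could be, and that no planned analysis would show by how much.

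**What to change.** In SAP 8.4.1.1, pre-specify an ANCOVA of baseline MUBADA SUVr on cognitive group, age and sex (using the recorded gender field), and report its adjusted difference and 95% interval beside the age-only result. State in advance which of the two is the lead estimate; either choice meets this point. Fixing both models before the comparison is run avoids choosing the covariate after an imbalance has been seen.

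In SAP 8.3.1, state that sex is tabulated by CI and CN. It would help to show this for the efficacy population too, because the baseline table uses the safety population while the ANCOVA uses subjects with an available SUVr.

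The change needs no new data. It costs one degree of freedom, a sentence or two in the SAP and one extra row of output. If sex proves unrelated to SUVr, the standard error is about 2% larger at a 20-point imbalance and about 8% larger at 40 points.

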8.4.1.2 Correlation between MMSE and MUBADA SUVr

Depending on available data, Spearman's correlation coefficient will be used to measure the relationship between MMSE and MUBADA SUVr at baseline. This relationship will also be presented in a scatter plot.

8.5 Analysis of Safety

8.5.1 Exposure

The total dose administered (MBq) of flortaucipir will be summarized for each visit in a table using descriptive statistics and presented in a listing.

